### 7.3.5 Reporting of Pregnancy

If, following initiation of the investigational product, it is subsequently discovered that a study participant is pregnant or may have been pregnant at the time of investigational product exposure, including during at least 5 half-lives after product administration, the investigational product will be permanently discontinued in an appropriate manner (eg, dose tapering if necessary for participant).

The investigator must immediately notify [[contact]](mailto:[contact]) of this event via either the CIOMS, MedWatch or appropriate Pregnancy Surveillance Form in accordance with SAE reporting procedures.

Protocol-required procedures for study discontinuation and follow-up must be performed on the participant.

Follow-up information regarding the course of the pregnancy, including perinatal and neonatal outcome and, where applicable, offspring information must be reported on the CIOMS, MedWatch, BMS Pregnancy Surveillance Form, or approved site SAE form. A BMS Pregnancy Surveillance Form may be provided upon request.

Any pregnancy that occurs in a female partner of a male study participant should be reported to BMS. Information on this pregnancy will be collected on the Pregnancy Surveillance Form. In order for Sponsor or designee to collect any pregnancy surveillance information from the female partner, the female partner must sign an informed consent form for disclosure of this information.

## 7.4 Routine Adverse Event Reporting

All Grade 2 or higher Adverse Events (excluding non-clinically significant laboratory values) **must** be reported in routine study data submissions to the Overall PI on the toxicity case report forms. **AEs reported through expedited processes (e.g., reported to the IRB, FDA, etc.) must also be reported in routine study data submissions.**

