Note: Rule out non-inflammatory causes. If non-inflammatory cause, treat accordingly and continue protocol therapy. Evaluate with imaging and pulmonary consultation as clinically appropriate.		
Grade of Pneumonitis	Management	Follow-Up
Grade 1	Consider delay of protocol therapy  Monitor for symptoms every 2-3 days  Consider Pulmonary and ID consults	Re-image at least every 3 weeks  If worsens:  Treat as Grade 2 or ≥ Grade 3.
Grade 2	Delay protocol therapy  Obtain Pulmonary and ID consults as clinically appropriate  Monitor symptoms daily, consider hospitalization  Administer 1.0 mg/kg/day methylprednisolone IV or oral equivalent  Consider bronchoscopy, lung biopsy as clinically appropriate	Consider reimaging weekly  If improves:  Re-imaging every 1-3 weeks, monitoring symptoms every 2-3 days.  When symptoms return to near baseline, taper steroids over at least 1 month and then resume protocol therapy and consider prophylactic antibiotics  If not improving after 2 weeks or worsening:

Table 6: Pulmonary Adverse Event Management		
Note: Rule out non-inflammatory causes. If non-inflammatory cause, treat accordingly and continue protocol therapy. Evaluate with imaging and pulmonary consultation as clinically appropriate.		
Grade of Pneumonitis	Management	Follow-Up
		Treat as $\geq$ Grade 3.
$\geq$ Grade 3	Permanently discontinue protocol therapy Hospitalize as clinically indicated Obtain pulmonary and ID consults as appropriate Administer 2-4 mg/kg/day methylprednisolone IV or IV equivalent Add prophylactic antibiotics for opportunistic infections Consider bronchoscopy, lung biopsy	If improves to baseline: Taper steroids over at least 6 weeks. If not improving after 48 hours or worsening: Add additional immunosuppression.
Patients on IV steroids may be switched to an equivalent dose of oral corticosteroids (e.g. prednisone) at start of tapering or earlier, once sustained clinical improvement is observed. Lower bioavailability of oral corticosteroids should be taken into account when switching to the equivalent dose of oral corticosteroids.		

Table 7: Hepatic Adverse Event Management		
Note: Rule out non-inflammatory causes. If non-inflammatory cause, treat accordingly and continue protocol therapy. Consider imaging for obstruction.		
Grade of Liver Test Function	Management	Follow-Up

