$\geq$ Grade 3	Permanently discontinue protocol therapy  Obtain neurology consult as clinically appropriate  Treat symptoms per local guidelines  Administer 1.0-2.0 mg/kg/day methylprednisolone IV or IV equivalent  Add prophylactic antibiotics for opportunistic infections	If returns to Grade 2: Taper steroids over at least 1 month.  If worsens or atypical presentation: Consider IVIG or other immunosuppressive therapies per local guidelines.

Patients on IV steroids may be switched to an equivalent dose of oral corticosteroids (e.g. prednisone) at start of tapering or earlier, once sustained clinical improvement is observed. Lower bioavailability of oral corticosteroids should be taken into account when switching to the equivalent dose of oral corticosteroids.
 
* Discontinue for any grade myasthenia gravis, Guillain-Barre syndrome, treatment-related myelitis, or encephalitis
		

Table 11: Pancreatic Adverse Event Management		
Note: Rule out non-inflammatory causes. If non-inflammatory cause, treat accordingly and continue protocol therapy.		
Grade of Amylase or Lipase Elevation, Pancreatitis	ManagementB	Follow-Up
	Continue protocol therapy.	Resume routine protocol monitoring.

Table 11: Pancreatic Adverse Event Management		
Note: Rule out non-inflammatory causes. If non-inflammatory cause, treat accordingly and continue protocol therapy.		
Grade of Amylase or Lipase Elevation, Pancreatitis	ManagementB	Follow-Up
Asymptomatic Grade 1 A	Monitor amylase and lipase weekly until resolution to baseline.	If worsens: Treat as Grade 2-3 or 4.
Asymptomatic Grade 2-3 A	Delay protocol therapy. Monitor amylase and lipase weekly until resolution to baseline.	If improves to baseline: Resume protocol therapy and routine protocol monitoring. If worsens: Treat as Grade 4.
Asymptomatic Grade 4 A	Permanently discontinue protocol therapy. Monitor amylase and lipase weekly until resolution.	Monitor patient until resolution to baseline.
Any Symptomatic Elevations in Amylase/Lipase, Pancreatitis	Permanently discontinue protocol therapy. Consider GI consult as clinically appropriate. Administer supportive care.	Monitor patient until resolution to baseline.

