### 7.3.4 Expedited Reporting to BMS

SAEs, whether related or not related to study drug, and pregnancies must be reported to BMS within 24 business hours of the awareness of the event. SAEs must be recorded on a Medwatch Form 3500A.

**SAE Email Address:** [contact]

**SAE [contact]

Adverse events generally considered serious are those that occur at any dose during any use of BMS product that:

- Results in death
- Is life-threatening (defined as an event in which the participant was at risk of death at the time of the event; it does not refer to an event which hypothetically might have caused death if it were more severe)
- Requires inpatient hospitalization or causes prolongation of existing hospitalization
- Results in persistent or significant disability/incapacity
- Is a congenital anomaly/birth defect
- Is an important medical event (defined as a medical event(s) that may not be immediately life-threatening or result in death or hospitalization but, based upon appropriate medical and scientific judgment, may jeopardize the subject or may require intervention [eg, medical, surgical] to prevent one of the other serious outcomes listed in the definition above.) Examples of such events include, but are not limited to, intensive treatment in an emergency room or at home for allergic bronchospasm; blood dyscrasias or convulsions that do not result in hospitalization.)
- Suspected transmission of an infectious agent (eg, pathogenic or nonpathogenic) via the study drug is an SAE.

A planned medical or surgical procedure is not, in itself, an SAE. Generally, any events that meet any of the seriousness criteria listed above and that are caused by progression of the disease under the study (metastatic breast cancer) are not reportable. Any instance of pregnancy, overdose, potential drug-induced liver injury (DILI), and secondary malignancies, though not necessarily considered serious per these definitions should be reported as SAEs.

If only limited information is initially available, a follow-up report is required and should include the same investigator term(s) initially reported.

If an ongoing SAE changes in its intensity or relationship to study drug or if new information becomes available, a follow-up SAE report should be sent within 24 hours of awareness to BMS (or designee) using the same procedure used for transmitting the initial SAE report.

All SAEs should be followed to resolution or stabilization.

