#### Safety and tolerability

All patients will be evaluable for toxicity from the time of their first treatment with any study agent. Toxicity will be graded according to NCI CTCAE, Version 5.0. Toxicities will be summarized by maximum grade and by treatment arm. Incidence rate of each toxicity will be reported with 95% exact CI. The incidence rates of any grade 3+ toxicity will be compared between two arms using Fisher's exact test.

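### Section 7.4 does not require non-serious Grade 1 events on the toxicity forms, yet 13.4 reports each toxicity's incidence and maximum grade with no stated floor

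*Combined protocol and SAP*

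**What the plan says.** **Collection.** Section 7.4 requires "All Grade 2 or higher Adverse Events (excluding non-clinically significant laboratory values") to "be reported in routine study data submissions to the Overall PI on the toxicity case report forms". Its next sentence widens this: "AEs reported through expedited processes (e.g., reported to the IRB, FDA, etc.) must also be reported in routine study data submissions". No grade limit is attached to that second route. Section 7.3.4 states that "SAEs, whether related or not related to study drug, and pregnancies must be reported to BMS", and it defines an SAE by seriousness rather than grade.

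**Analysis.** Section 13.4, under Safety and tolerability, says "Toxicities will be summarized by maximum grade and by treatment arm" and "Incidence rate of each toxicity will be reported with 95% exact CI". Neither sentence gives a lower grade limit. The only threshold in that paragraph is Grade 3+, for a separate rate.

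**Grade 1 events that can change treatment.** In Section 6.1, the Grade 1 pneumonitis row of Table 6 reads "Consider delay of protocol therapy". Table 9 provides for a delay, and for considering methylprednisolone, when Grade 1-2 rash persists or recurs. The footnote to Table 10 reads "Discontinue for any grade myasthenia gravis, Guillain-Barre syndrome, treatment-related myelitis, or encephalitis". Section 6.2 lets the treating investigator hold either drug for a toxicity at any grade. Section 5.5 requires the reason and date of removal from protocol therapy on a CRF and in the trial management system.

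**The concern.** The data-collection rule and the analysis rule do not share a grade floor. Where the protocol wants a floor it states one: Grade 3+ in 13.4 and Grade 2 or higher for diarrhea in objective 1.4.15. An incidence of each toxicity with no floor is therefore naturally read as covering all grades, which the required data cannot support. Section 7.4 sets a minimum and does not bar Grade 1 entries, so sites may also differ. The Grade 1 column of the maximum-grade table would then be partly filled and hard to interpret.

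At stake is objective 1.3.1, safety and tolerability, which heads the secondary objectives. A reader may set the reported rates beside figures such as the 33.9% skin-reaction rate for this combination in Section 2.5.3.1. That figure appears to be all-grade, because Grade 3 or 4 select events are given separately there. A treatment delay could also appear in the dosing record with no matching event on the toxicity forms.

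**Working it through.** The plan states no figure on this point, so there is nothing to reproduce. The check sets the rules side by side and then shows how the bias behaves.

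**1. Does a Grade 1 event have to be on the toxicity form?**

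| Event | Required? | Source |
|---|---|---|
| Grade 1, serious | Yes, through the expedited route | 7.3.4 and 7.4 |
| Grade 1, non-serious, no treatment change | No | 7.4 |
| Grade 1, non-serious, leading to delay or hold | No | 7.4, with 6.1 Tables 6 and 9, and 6.2 |
| Grade 1, non-serious, leading to permanent removal | No, but the reason for removal goes on a CRF | 5.5 |

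The table of reportable events in 7.3.1 starts at Grade 2, so it gives no further route for a non-serious Grade 1 event.

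**2. How is such a patient counted?** Section 13.6.2 treats a patient with no adverse events as having a safety assessment. A patient whose worst event is an unentered Grade 1 therefore stays in the denominator and counts as unaffected.

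**3. Direction and form of the bias.** Let *t* be the true all-grade rate and *s* the share of affected patients whose worst grade is 1 and whose event is not entered. Then

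observed rate = *t* × (1 − *s*).

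Inputs: *n* = 30 is the target enrollment in 13.1. The values *t* = 40% (12 of 30) and *s* = 25%, 50% and 75% are assumptions; the documents give neither. Intervals are Clopper-Pearson: the lower limit is the 0.025 quantile of Beta(*x*, *n* − *x* + 1), and the upper limit is the 0.975 quantile of Beta(*x* + 1, *n* − *x*).

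| Assumed *s* | Patients shown | Rate | 95% exact CI |
|---|---|---|---|
| 0 (full capture) | 12/30 | 40.0% | 22.7% to 59.4% |
| 25% | 12 × 0.75 = 9/30 | 30.0% | 14.7% to 49.4% |
| 50% | 12 × 0.50 = 6/30 | 20.0% | 7.7% to 38.6% |
| 75% | 12 × 0.25 = 3/30 | 10.0% | 2.1% to 26.5% |

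At *s* = 50% and above, the interval no longer contains the 40.0% that full capture would show. If some sites enter Grade 1 events voluntarily, the shortfall is smaller but uneven across sites.

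The same formula applied to the cited 33.9%, with assumed shares of 25% and 60%, gives 33.9% × 0.75 = 25.4% and 33.9% × 0.40 = 13.6%.

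**4. What does not move.** Grade 2+ and Grade 3+ rates of clinical events use only events that 7.4 requires. The response-rate endpoint and the stage-one rule do not use toxicity forms.

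**5. Treatment-changing events.** A non-serious Grade 1 pneumonitis that leads to a delay, a persistent or recurrent Grade 1 rash, or a discretionary hold under 6.2 is not required on the toxicity form. Steroid use need not reveal it either: Section 5.4.1 and Study Calendar footnote d place medications in the electronic medical record and do not mention a CRF.

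**The case against.** The best defense is that a Grade 2 floor is a legitimate design choice and fits the rest of the protocol. The reportable-event table in 7.3.1 starts at Grade 2, the monitoring committee in 12.2 receives unexpected events of Grade 2 or higher, and objective 1.4.15 uses Grade 2 diarrhea. Section 13.4 never uses the term any-grade. If its tables are understood as Grade 2+, the clinical event rates are correct and need only a label. No comparison with outside rates is planned. This stands, and it is why the fix keeps the floor.

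Three stronger readings are tempting, and the documents do not support them.

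- A reader might infer that nothing below Grade 2 reaches the forms. The second sentence of the 7.4 rule brings in expedited events at any grade, and 7.4 is a minimum.
- A reader might infer that Grade 1 events that end treatment are lost. Section 5.5 puts the reason for removal on a CRF, although it does not promise a graded event term. The neurological conditions in Table 10 could also plausibly qualify as important medical events under 7.3.4, and so be captured as SAEs. They are the weaker example.
- A reader might take one of the percentages above as the expected bias. Section 2.4.2 says most nivolumab events were low grade but pools Grades 1 and 2, so it gives no Grade 1 share. The 33.9% is a pooled category of select skin events from a lung cancer trial.

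What the defense does not answer is that 13.4 states no floor, and that a non-serious Grade 1 event behind a delay or hold has no required place on the toxicity form.

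**Conclusion.** The mismatch holds in a narrow form. Section 7.4 does not require non-serious Grade 1 events on the toxicity forms, while 13.4 reports incidence and maximum grade with no stated floor. If those rates are presented as overall incidence, they are understated by the share of affected patients whose worst grade is 1. The direction is certain wherever such events go unentered. The size cannot be derived from the documents, and the 30.0% to 10.0% shown for a true 40.0% rests wholly on assumed shares.

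The practical gap is non-serious Grade 1 events that lead to a delay or hold. It would go too far to say that treatment-changing Grade 1 events will in general be missing: serious ones are captured, and reasons for permanent removal are recorded. The point is minor. It bears on the safety and tolerability objective only, and it is cheap to correct.

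**What to change.** 1. In 7.4, add that any adverse event of any grade that leads to delay, hold or discontinuation of either drug, or to systemic corticosteroids, must also be entered on the toxicity form.
2. In 13.4, define the incidence and maximum-grade tables as Grade 2 or higher, with the same laboratory exclusion as 7.4, and list the treatment-changing Grade 1 events separately.

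These changes do not recover overall incidence or complete a Grade 1 column, and the tables should not claim to show either. The first change supplies the events behind treatment interruptions; the second makes the reported rates match what was collected. The cost is one sentence in each section and a few extra form entries. Adverse events are already evaluated at every treatment visit in the Study Calendar, so no visits are added, and no clinical management rule changes. The change is best made early, because unentered Grade 1 events could later be recovered only by chart review.

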## 8. PHARMACEUTICAL INFORMATION

A list of the adverse events and potential risks associated with the investigational agents administered in this study can be found in Section 7.1.

### 8.1 Nivolumab

#### 8.1.1 Description

Nivolumab is also referred to as BMS-936558-01 or BMS-936558. Nivolumab is a soluble protein consisting of 4 polypeptide chains, which include 2 identical heavy chains and 2 identical light chains. The physical and chemical properties of nivolumab are provided in Table 8.1.1 below. The geometric mean of terminal T-HALF was 25.6 days and the typical clearance was 8.8 mL/h, which are consistent with those of full human immunoglobulin antibodies.

**Table 14: Nivolumab Physical and Chemical Properties**

BMS Number	BMS-936558-01
Other Names	Nivolumab, BMS-936558, MDX1106, ONO-4538, anti-PD-1
Molecular Weight	146,221 daltons
Appearance	Clear to opalescent, colorless to pale yellow liquid, light (few) particulates may be present
Solution pH	5.5 to 6.5

#### 8.1.2 Storage and Stability

Vials of Nivolumab injection must be stored at 2°-8°C (36°-46°F) and protected from light, freezing and shaking. Shelf-life surveillance of the intact vials is ongoing.

The administration of undiluted and diluted solutions of Nivolumab must be completed within 24 hours of preparation. If not used immediately, the infusion solution may be stored up to 24 hours in a refrigerator at 2°-8°C (36°-46°F) and a maximum of 8 hours of the total 24 hours can be at room temperature (20°-25°C, 68°-77°F) and room light. The maximum 8-hour period under room temperature and room light conditions includes the product administration period.

**CAUTION:** The single-use dosage form contains no antibacterial preservative or bacteriostatic agent. Therefore, it is advised that the product be discarded 8 hours after initial entry.

#### 8.1.3 Compatibility

No incompatibilities between Nivolumab injection and polyvinyl chloride (PVC), non-PVC/non-DEHP (di(2-ethylhexyl)phthalate) IV components, or glass bottles have been observed.

#### 8.1.4 Handling

Qualified personnel, familiar with procedures that minimize undue exposure to themselves and the environment, should undertake the preparation, handling, and safe disposal of the chemotherapeutic agent in a self-contained and protective environment.

#### 8.1.5 Availability

Nivolumab is available as 100 mg vials (10 mg/mL) with a 0.7mL overfill. It is supplied in 10 mL type I flint glass vials, with butyl rubber stoppers and aluminum seals.

#### 8.1.6 Preparation

Nivolumab is available as 100 mg vials (10 mg/mL), which include an overfill. It is supplied in 10 mL type I flint glass vials, with butyl stoppers and aluminum seals. Nivolumab injection can be infused undiluted (10 mg/mL) or diluted with 0.9% Sodium Chloride Injection, USP or 5% Dextrose, USP to concentrations no less than 0.35 mg/mL.

#### 8.1.7 Administration

Nivolumab will be delivered in infusion bags with IV infusion lines over 60 minutes (+/- 5 minutes) using a volumetric pump with 0.2 to 1.2 micron pore size, low-protein binding polyethersulfone membrane in-line filter. Weight for dosage calculations should be done per institutional standards of practice. Re-calculation of dosage for fluctuations in body weight should be made in accordance with institutional guidelines.

#### 8.1.8 Ordering

Nivolumab will be provided by BMS. Each participating institutions is responsible for completing the applicable drug supply forms to receive re-supply of Nivolumab for the duration of the study. Except in very unusual circumstances, each participating institution will order the study agent(s). A participating site may order the agent(s) only after the initial IRB approval for the site has been forwarded by the Coordinating Center to the supplier.

#### 8.1.9 Accountability

The investigator, or a responsible party designated by the investigator, should maintain a careful record of the inventory and disposition of the agent using the NCI Drug Accountability Record Form (DARF) or another comparable drug accountability form. (See the NCI Investigator's Handbook for Procedures for Drug Accountability and Storage.)

#### 8.1.10 Destruction and Return

At the end of the study, unused supplies of nivolumab should be destroyed according to institutional policies. Destruction will be documented in the Drug Accountability Record Form.

## 8.2 Ipilimumab

### 8.2.1 Description

Ipilimumab (BMS-734016, MDX-010) is a fully human IgG1 $\kappa$  consisting of 4 polypeptide chains; 2 identical heavy chains primarily consisting of 447 amino acids each with 2 identical kappa light chains consisting of 215 amino acids each linked through inter-chain disulfide bonds.

**Table 15: Ipilimumab Physical and Chemical Properties**

BMS Number	BMS-734016
Other Names	BMS-734016, MDX-010, YERVOY
Molecular Weight	147, 991 Daltons
Appearance	Clear to slightly opalescent, colorless to pale yellow liquid, may contain particiles
Solution pH	7.0
pI	The isoelectric focusing analysis generates a banding batter in the pI range of 8.5 to 8.8, with the major isoform at an apprcimate pI of 8.7

### 8.2.2 Form

Ipilimumab injection, 200 mg/40 mL (5 mg/mL), is formulated as a clear to slightly opalescent, colorless to pale yellow, sterile, nonpyrogenic, single-use, isotonic aqueous solution that may contain particles. Ipilimumab injection, 200 mg/40 mL, is supplied in 50-cc Type I flint glass vials, respectively, stoppered with gray butyl stoppers and sealed with aluminum seals. The drug product is formulated at a concentration of 5 mg/mL at a pH of 7.0.

### 8.2.3 Storage and Stability

Ipilimumab Injection, 200 mg/40 mL (5 mg/mL), must be stored refrigerated (2°C to 8°C) and protected from light. Ipilimumab injection must not be frozen.

Partially used vials or empty vials of ipilimumab injection should be discarded at the site according to appropriate drug disposal procedures.

Ipilimumab injection may be stored undiluted (5 mg/mL) or following dilution in 0.9% Sodium Chloride Injection, USP or 5% Dextrose Injection in PVC, non-PVC/non-DEHP or glass containers for up to 24 hours (at 2°C to 8°C) or room temperature/room light.

